8.3 Concomitant Medications

Concomitant medications will be coded using the latest version of the World Health Organization (WHO) drug dictionary. The number and percentage of subjects taking concomitant medications prior to the 24-month open-label treatment period, during the 24-month open-label treatment period, and during the follow-up period will be respectively tabulated by drug class and medication generic name, based on the Safety Sample.

8.4 Extent of Exposure to the IMP

The extent of exposure to IMP will be summarized separately for the Safety Sample for the 24-month open-label treatment period, and for the Safety Sample for the conversion period.

8.4.1 Exposure Data for the 24-month Open-label Treatment Period

An individual subject's days of exposure to IMP for the open-label treatment period is calculated as: date of last dose in the open-label treatment period – date of first dose in the open-label treatment period + 1, regardless of any treatment gaps such as dose interruptions or omissions. An individual subject's average daily dose (unit: mg/day) will be calculated as: total dose (in mg) divided by days of exposure, where total dose is the summation of the actual daily doses (in mg) taken over the entire open-label treatment period.

The number and percentage of subjects having had IMP exposure of ≥ 3 , 6, 12, 15, 18, and 24 months will be respectively tabulated and the descriptive statistics (eg, mean) of the average daily dose will be calculated based on the subset of subjects having had exposure in the corresponding exposure interval (eg, " ≥ 6 months" refers to a semi-open exposure interval).

For calculating the percentage, the number of subjects having had any IMP exposure in the 24-month open-label treatment period will be used as the denominator.

Days of exposure and the average daily dose will be summarized for the Safety Sample for the 24-month open-label treatment period by using descriptive statistics (such as mean, SD).

8.4.2 Exposure Data for the 1- to 4-week Cross-titration Conversion Period

An individual subject's days of exposure to IMP for the conversion period is calculated as: date of last dose in the conversion period – date of first dose in the conversion + 1, regardless of any treatment gaps such as dose interruptions or omissions. An individual subject's average daily dose (unit: mg/day) will be calculated as: total dose (in mg) divided by days of exposure, where total dose is the summation of the actual daily doses (in mg) taken over the conversion period.

The number and percentage of subjects exposed to IMP will be tabulated by trial week. The average daily dose will be calculated for each week and will be summarized by trial week.

9 Analysis and Reporting of Efficacy Outcomes

All efficacy analyses specified in this section will be performed on the Efficacy Sample. For each efficacy variable, the analysis (eg, data summary) and reporting will be provided for the 24-month open-label treatment period only, since there is no efficacy assessment in the conversion period on the de novo subjects that underwent a cross-titration conversion.

For both rollover and de novo subjects, efficacy assessments will be collected at Week 4 and Months 2, 3, 4, 6, 8, 10, 12, 18, and 24 during the 24-month open-label treatment period. Additionally, for the de novo subjects, efficacy assessments (with the exception of the Clinical Global Impression – Improvement scale [CGI-I]) will also be collected at Day 1 of the 24-month open-label treatment period.

All efficacy assessments will be treated as secondary outcomes (endpoints) for this trial.

9.1 Secondary Endpoints

The secondary endpoints for this trial pertain to the following efficacy variables: PANSS Total Score, PANSS Positive subscale score, PANSS Negative subscale score, CGI-S score, and CGI-I score. Each of these 5 variables and the change from baseline in each of them (except the CGI-I score) will be summarized on the OC data by visit and additionally on the LOCF data for the last assessment visit by using descriptive statistics for continuous variables. Note that change from baseline in CGI-I score is not meaningful and hence will not be calculated for the statistical summary.

Additionally, the number and percentage of subjects having had either “very much improved” (with CGI-I score of 1) or “much improved” (with CGI-I score of 2) in the variable CGI-I score will be tabulated on the OC data by visit and on the LOCF data for the last assessment visit.

The number and percentage of responders (defined as a reduction of $\geq 30\%$ from baseline to the last visit in PANSS Total Score or having a CGI-I score of 1 or 2 at the last visit) will be provided.

The PANSS Total Score will also be summarized for gender, race (White, Black or African American, American Indian or Alaska Native, Asian, Native Hawaiian or Other Pacific Islander, other), region (US, Europe [continent], Mexico) and age (< 15 years, ≥ 15 years, based on Trial 331-10-236 entry) subgroups.

Refer to [Section 10.3](#) for the definition of baseline value. Note that the CGI-I assessment is not administered at the screening or Day 1 visits in the 24-month open-label treatment period; thus, there is no baseline value for the CGI-I score.

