|                      | 
 
• Mean change from baseline on the AIMS, Simpson-Angus Scale (SAS), and Barnes Akathisia Rating Scale (BARS)
 
• Analysis of potential suicide events recorded on the C-SSRS
 
• Comprehensive psychotropic side effects as assessed by UKU side effect rating scale
 
• The frequency of symptom items for the clinician-administered NY-AACENT
 
• Baseline and postbaseline Tanner Staging Scale data
 
• Time to discontinuation due to AE
 
 
The secondary efficacy endpoints are as follows:
 
 
• Change in the PANSS Total Score and the Positive and Negative Subscale Scores
 
• Change in the CGAS Score
 
• CGI-S scale
 
• CGI-I scale
 
  |
| Statistical Methods: | 
Sample size was not determined by a formal computation to achieve a target power. Sample size was planned to attain at least 100 subjects completing 1 year of exposure to open-label brexpiprazole.
 
Descriptive statistics will be provided for all efficacy and safety variables. Continuous variables will be summarized by tabulations of mean, median, range, and standard deviation. Tabulations of frequency distributions will be provided for categorical variables. A Kaplan-Meier curve will be plotted for the time to discontinuation due to AE variable.
 
Safety tabulations will include duration on brexpiprazole, the frequency of AEs, serious TEAEs, ECGs, vital sign abnormalities, weight, BMI, waist circumference changes, laboratory abnormalities and therapy discontinuations. The efficacy variables (for subjects with schizophrenia: PANSS Total score, PANSS Positive and Negative Subscales, and CGAS) will be summarized by change from baseline over time. Tanner Staging Scale data will be summarized using shift tables. The incidence of suicidality, suicidal behavior and suicidal ideation will be summarized from the data recorded on the C-SSRS forms, and results will be summarized by visit. Other outcomes including PANSS Cognitive Subscale will be summarized for their change from baseline by visit.
 |

|                 |   |
|-----------------|---|
|                 | 
No inferential statistical analyses are planned for this open-label trial. All analyses will be exploratory and conducted only to report the long-term safety of brexpiprazole for all subjects who are administered at least 1 dose of brexpiprazole.
   |

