### **3.5.2.2 Secondary Efficacy Endpoints**

The secondary efficacy endpoints are as follows:

- Change from baseline in the Positive and Negative Syndrome Scale (PANSS) Total Score and the Positive and Negative Subscale Scores
- Change from baseline in the Children's Global Assessment Scale (CGAS) Score
- Clinical Global Impression Severity (CGI-S) scale
- Clinical Global Impression Improvement (CGI-I) scale

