### **7.3.2 Secondary Endpoint Analysis**

Descriptive statistics will be provided for mean change from baseline in PANSS Total Score, PANSS Positive and Negative Subscales, and CGAS scores for subjects with schizophrenia. The analysis will be carried out on the Efficacy Sample. Descriptive statistics will be summarized at each trial visit using the observed cases (OC) data set and at the last visit using the last observation carried forward (LOCF) data set.

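### SAP 9.1 limits the secondary efficacy summaries to five variables and omits CGAS, so no post-baseline analysis is specified for this protocol secondary endpoint

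*SAP*

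**What the plan says.** **Protocol.** Section 3.5.2.2 lists as a secondary efficacy endpoint "Change from baseline in the Children's Global Assessment Scale (CGAS) Score". Section 7.3.2 gives its analysis: "Descriptive statistics will be provided for mean change from baseline in PANSS Total Score, PANSS Positive and Negative Subscales, and CGAS scores", on the Efficacy Sample, with OC data at each visit and LOCF data at the last visit. The Statistical Methods part of the synopsis agrees: "PANSS Total score, PANSS Positive and Negative Subscales, and CGAS) will be summarized by change from baseline over time".

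**SAP.** Section 9.1 ties the secondary endpoints to "PANSS Total Score, PANSS Positive subscale score, PANSS Negative subscale score, CGI-S score, and CGI-I score". It then specifies the OC by-visit and LOCF last-visit summaries for "Each of these 5 variables and the change from baseline in each of them", with CGI-I exempted from the change calculation. Just before this, Section 9 says in general terms: "All efficacy assessments will be treated as secondary outcomes (endpoints) for this trial". On timing it says "efficacy assessments will be collected at Week 4 and Months 2, 3, 4, 6, 8, 10, 12, 18, and 24".

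CGAS appears in four other places in the SAP: the abbreviation list, the baseline characteristics in Section 7, the baseline psychiatric evaluation in 7.3, and the list of parameters in 10.5 for which a last-visit value is derived by LOCF.

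**The concern.** SAP 9.1 is the section from which the efficacy tables would be programmed. Its list is closed by a count, so CGAS cannot be read into it as an unstated example. A programmer who follows 9.1 literally produces no CGAS table after baseline, although the protocol commits to one. The result would be either a pre-specified endpoint without its summary in the study report, or a CGAS table made outside the plan.

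CGAS rates psychological, social and school functioning (protocol 3.7.2.2), while PANSS and CGI rate symptoms and global illness. The protocol's rationale (2.1) raises reduced functioning in adulthood as a consequence of early-onset disease, so the missing summary is the one efficacy measure that addresses it.

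**Working it through.** No power, alpha or sample-size formula applies, because the trial is descriptive. The check is a count and a comparison of the two documents.

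**1. The SAP's own figure.** PANSS Total, PANSS Positive, PANSS Negative, CGI-S, CGI-I: 3 + 2 = 5. This matches the five stated in SAP 9.1.

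**2. The protocol's list (3.5.2.2).** PANSS Total, PANSS Positive, PANSS Negative, CGAS, CGI-S, CGI-I: 3 + 1 + 2 = 6. The difference is 6 − 5 = 1, and the variable missing from the SAP is CGAS. It is also one of only four variables that protocol 7.3.2 names for analysis.

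**3. What each SAP section provides for CGAS.**

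| SAP section | Content on CGAS | Post-baseline summary specified? |
|---|---|---|
| 7 and 7.3 | Baseline value summarised | No |
| 9, opening text | Not named; efficacy assessments in general are secondary | No |
| 9.1 | Not in the list of five | No |
| 9.2 | Not named; all efficacy data reported at the interim | No |
| 9.4 | Not named; scoring rules for PANSS and CGI only | No |
| 10.5 | In the list for LOCF last-visit derivation | Value derived, but no table uses it |

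The number of specified post-baseline or change-from-baseline CGAS summaries is 0.

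**4. Effect of adding CGAS.** Variables summarised: 5 + 1 = 6. Variables with change from baseline (all but CGI-I): 5 − 1 = 4 now, and 6 − 1 = 5 afterwards.

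**5. Visits.** Protocol Tables 3.7-1 and 3.7-2 schedule CGAS after baseline at Weeks 1, 2, 4 (3 visits) and Months 2, 3, 4, 6, 8, 10, 12, 15, 18, 21, 24 (11 visits): 3 + 11 = 14, which is every open-label clinic visit. The visit sentence in SAP Section 9 has Week 4 plus nine months: 1 + 9 = 10. The four not mentioned are Weeks 1 and 2 and Months 15 and 21. The ten listed visits are the PANSS and CGI schedule, so the sentence appears to have been written with those scales in mind.

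SAP 9.4 uses OC data for all protocol-scheduled visits, and Table 10.2-1 already has windows for the four: days 2 to 10, 11 to 20, 413 to 496 and 581 to 664. The sentence is incomplete for CGAS, but the analysis rules do not shut these visits out.

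**The case against.** The best defence is that the SAP does not abandon CGAS. Section 10.5 derives a last-visit value from post-baseline CGAS data and says that by-visit analyses generally include the derived last visit. Section 9 treats all efficacy assessments as secondary outcomes, and the protocol classes CGAS as one. Section 9.2 promises that all efficacy data will be reported at the interim. Section 1 presents the SAP as an expansion of the protocol's statistical section, where the CGAS summaries are set out.

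This makes an oversight more likely than a decision, but it does not supply the analysis. The convention in 10.5 adds a last visit to a by-visit analysis that already exists, and none is specified for CGAS. The statements in 9 and 9.2 name no summary and do not override a list closed by number. What 10.5 does show is that the SAP is inconsistent with itself.

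Four stronger readings are tempting, and the documents do not support them:

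- **That CGAS will go wholly unreported.** Baseline CGAS is summarised, and the protocol's plan for the change analysis still stands. The gap is in what the SAP specifies.
- **That the endpoint was dropped without explanation.** The SAP's contents list a Section 12 on amendment history that is not in the text available for review, so this cannot be verified.
- **That CGAS is the trial's only functional measure, taken at every visit.** SAP 8.2.6.1 also summarises UKU interference with daily performance and NY-AACENT items with functional impairment. CGAS is the only functional efficacy scale, and it is not rated at the conversion-period visits.
- **That four CGAS visits are excluded from analysis.** The protocol-visit rule in SAP 9.4 and the windows in Table 10.2-1 accommodate them. The short visit list is a symptom of the same omission and adds no separate loss.

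**Conclusion.** The point holds. SAP 9.1 is wrong as written, and this is more than missing detail: following its stated rule omits the post-baseline analysis of one of six protocol secondary efficacy endpoints. The size is modest. CGAS is a descriptive secondary endpoint in a single-arm safety trial with no inferential analysis, so no primary endpoint, safety conclusion or sample-size figure changes. The visit list is a wording matter only.

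The conclusion assumes that protocol 3.5.2.2 and 7.3.2 still express the sponsor's intention, and that the unseen SAP amendment history does not record a justified removal. If it does record one, what remains is to reconcile 9.1 with 10.5 and with the protocol.

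**What to change.** In SAP 9.1, add CGAS to the named variables and change the count from five to six. Summarise CGAS as value and change from baseline, by visit on OC data and at the last visit on LOCF data, on the Efficacy Sample. This gives the last-visit value from 10.5 a table in which to appear. If the removal was intended, say so and justify it, and take CGAS out of the list in 10.5.

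As a wording correction, note in SAP Section 9 that CGAS is also collected at Weeks 1 and 2 and Months 15 and 21. Table 10.2-1 needs no change.

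The cost is a few words in the SAP and one table. The protocol already schedules the assessments, so no new data collection is needed.

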9.2 Interim Analysis

There will be an interim data reporting when approximately 100 subjects have had at least 6 months of exposure to the IMP in the 24-month open-label treatment period. An additional interim analysis will be performed approximately 6 months after the last subjects enters the trial.

All collected data including all safety and efficacy data will be reported for the interim data reporting. Database lock will be executed for the interim data reporting.

The final analysis will be performed upon completion of the trial. Database lock will be executed for the final analysis.

9.3 Multiplicity Adjustment

Not applicable.

9.4 Computational Details for Efficacy Scales

- 1) Observed case data will be used for the efficacy analyses for all scheduled (protocol-specified) visits, including the end-of-trial visit at Month 24, and LOCF data will be used only for the derived “last assessment visit”.

- 2) The PANSS Total Score is the sum of the rating scores over 7 positive scale items, 7 negative scale items, and 16 general psychopathology scale items from the PANSS panel in the eSource. If fewer than 24 of the 30 items are recorded, the PANSS Total Score will be unevaluable and thus set to missing. If 24 to 29 of the 30 items are recorded, the PANSS total is equal to the mean of the recorded items multiplied by 30 and rounded to the first decimal place.
- 3) The PANSS Positive subscale score is the sum of the rating scores over the 7 positive scale items from the PANSS panel in the eSource. The PANSS Negative subscale score is the sum of the rating scores for the 7 negative scale items from the PANSS panel in eSource. If fewer than 6 of the 7 items of the PANSS subscale scale are recorded, the PANSS subscale score will be unevaluable, thus missing. If 6 of the 7 items are recorded, the PANSS subscale score is equal to the mean of the recorded items multiplied by 7 and rounded to the first decimal place.
- 4) The CGI-S and CGI-I scores with a value (score) of zero (0) should be set to missing because the 0-score means “Not Assessed.”

10 Conventions and Handling of Missing Data

10.1 Trial Day

The trial day that is associated with an observation or an assessment will be used for purposes of (1) data reporting (eg, data listing), and (2) determining whether an AE is a TEAE relative to the trial period (eg, the conversion period or the open-label treatment period).

The trial day in relation to the open-label treatment period will be derived as follows:

- 1) Trial day = assessment date – first dose date + 1, for assessment date \geq first dose date;
- 2) Trial day = assessment date – first dose date, for assessment date $<$ first dose date.

Note that, the “first dose date” above refers to the first dose date for the open-label treatment. Specifically, for a rollover subject the first dose date is the next day after the last assessment visit (ie, the Week 6 visit) from the parent Trial 331-10-234, and for the de novo subject that underwent a 1- to 4-week conversion period, the first dose date (with respect to the open-label treatment period) coincides with the date of the last assessment visit in the conversion period.

The trial day in relation to the conversion period will be derived similarly and is applicable only to the de novo subjects that entered a cross-titration conversion period. Of course, in the derivation of the trial day in relation to the conversion period, the “first dose date” should be the first dose date upon entering the conversion period.

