## **3 Trial Design**

### **3.1 Type/Design of Trial**

This is a long-term, multicenter, open-label trial designed to examine the long-term safety and tolerability of brexpiprazole in adolescent subjects, ages 13 to 17 years at time of informed consent/assent and at the baseline (Day 1) visit of the open-label treatment period, with a *Diagnostic and Statistical Manual of Mental Disorders - Fifth Edition* (DSM-5) diagnosis of schizophrenia. Subjects from Trial 331-10-234 who turned 18 years old during that trial are also permitted to enroll in this trial. For de novo subjects who did not participate in Trial 331-10-234, the initial diagnosis of schizophrenia for this trial (as defined by DSM-5 criteria) should be made and documented by an adequately trained clinician (psychiatrist, or local medical equivalent who is experienced in treating adolescents with schizophrenia), and the diagnosis should

then be confirmed utilizing the Kiddie Schedule for Affective Disorders and Schizophrenia-Present and Lifetime version (K-SADS-PL) performed by an adequately trained rater at the time of screening. Rollover subjects will be considered as those who are able to rollover within  $\leq$  7 days of the Week 6 visit of Trial 331-10-234. Subjects who are only able to rollover from Trial 331-10-234 after  $>$  7 days from the Week 6 visit may be allowed to enter Trial 331-10-236 as de novo subjects following approval by the medical monitor.

The trial will be conducted on an outpatient basis. Hospitalization for psychosocial reasons (eg, homelessness or need for shelter that is unrelated to the subject's underlying psychiatric condition) will be considered outpatient status for the purpose of enrollment in Trial 331-10-236.

Subjects remaining in hospital at the Week 6 visit of Trial 331-10-234 (for other than psychosocial reasons) will be permitted to enroll in Trial 331-10-236 at the Week 6 visit of the double-blind trial if they are planned to be discharged from the hospital before the open-label treatment period Week 1 visit of Trial 331-10-236 and following approval by the medical monitor. De novo subjects hospitalized at the time of the Trial 331-10-236 screening visit will be permitted to be screened for the trial if they are planned to be discharged from the hospital prior to the baseline (Day 1) visit of the open-label treatment period and following approval by the medical monitor.

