#### **3.2.1 Rollover Subjects from Trial 331-10-234**

The first dose of open-label brexpiprazole will be taken 1 day after the last dose of double-blind IMP is taken in Trial 331-10-234 so that treatment continues without interruption. Whenever possible, it is anticipated that the last dose of the double-blind, phase 3 efficacy trial will be taken the day of the Week 6 visit of Trial 331-10-234 (ie, the day of the screening/baseline visit for the open-label trial). Subjects should not be dosed with using double-blind (331-10-234) and open-label (331-10-236) study medication on the same day.

Rollover subjects from Trial 331-10-234 will begin dosing with brexpiprazole 0.5 mg/day on Day 1, increasing to 1 mg/day on Day 5, and an optional increase to 2 mg/day if tolerated on Day 8 of the open-label treatment period. If the 2 mg dose is well tolerated, but the response is inadequate, weekly dose increases can be made in 1 mg increments to a maximum of 4 mg/day. Dose changes are allowed based on the clinical judgment of the investigator at scheduled or unscheduled visits according to his/her clinical judgment based on the subject's response to treatment. Daily dosing for this trial includes 1 mg, 2 mg, 3 mg, or 4 mg.

The dose of brexpiprazole may be decreased at any time based on the investigator's judgment after the start of the open-label treatment period. Dose decreases will occur in 1 mg decrements, with the frequency of the 1-mg decreases based upon tolerability. Those unable to tolerate the 1 mg daily dose of brexpiprazole must be withdrawn from the trial. The dosing strategy is summarized in [Table 3.2.1-1](#). Rechallenge with higher doses of brexpiprazole (ie, in 1 mg/day increments) is permitted following dose decreases, if clinically warranted based on the investigator's judgment.

If clinically indicated, subjects may return to the clinic for unscheduled visits if dose adjustments for brexpiprazole are required between scheduled visits. Dose adjustments must ultimately be made based upon the clinical judgment of the investigator as it relates to tolerability and therapeutic response.

| Table 3.2.1-1 Dose Adjustments for Brexpiprazole in the Open-label Treatment Period (Both Rollover Subjects from Trial 331-10-234 and Nonconversion De Novo Subjects) |                            |  |
|--|----------------------------|--|
| Trial Visit   | Dose Options        | Dose Changes  |

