### **3.4.2        Inclusion Criteria**

#### **3.4.2.1        Rollover Subjects**

Subjects are required to meet the inclusion criteria presented in [Table 3.4.2.1-1](#).

| Table 3.4.2.1-1      Inclusion Criteria for Rollover Subjects from Trial 331-10-234 |   |
|--|---|
| 1.   | Written informed consent/assent obtained from a legally acceptable representative (eg, guardian) or subject prior to the initiation of any protocol-required procedures. In addition, the subject must provide informed assent at screening and must be able to understand that he or she can withdraw from the trial at any time. All informed consent/assent procedures must be in accordance with the trial site's IRB/IEC and local regulatory requirements.  |
| 2.   | Ability, in the opinion of the principal investigator, of the subject and the subject's legally acceptable representative (eg, guardian) or caregiver(s) to understand the nature of the trial and follow protocol requirements, including the prescribed dosage regimens, tablet ingestion, and discontinuation of prohibited concomitant medications, to read and understand the written word in order to complete subject-reported outcomes measures, and to be reliably rated on assessment scales.   |
| 3.   | Male and female subjects 13 to 18 years of age, inclusive, at the time of informed consent/assent and at baseline. Subjects who turned 18 years old during Trial 331-10-234 are permitted in this trial.  |
| 4.   | Subjects who complete Trial 331-10-234 and who, in the opinion of the investigator, could potentially benefit from monotherapy treatment with oral brexpiprazole for schizophrenia. The baseline visit for Trial 331-10-236 coincides with the Week 6 visit of Trial 331-10-234. If the visit cannot be done within $\leq$ 7 days of the Week 6 visit of Trial 331-10-234 then the subject may be able to enter Trial 331-10-236 as a de novo subject following approval by the medical monitor.  |

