This statistical analysis plan (SAP) expands the statistical section of Protocol 331-10-236 Amendment 5,¹ and documents in detail the statistical methodologies and data analysis algorithms and the conventions to be applied to the analysis and reporting of safety and tolerability data collected in the trial. All amendments to the protocol have been taken into consideration in developing this SAP.

2 Trial Objectives

The primary objective of this trial is to assess the long-term safety and tolerability of oral brexpiprazole as monotherapy in adolescents (13 to 17 years old) with schizophrenia. Efficacy outcomes such as the Positive and Negative Syndrome Scale (PANSS) ratings over a long-term period will also be assessed, but of secondary interest.

[figure not shown]
3 Trial Design

This is a long-term (24-month), multicenter, single-arm, open-label trial designed to examine the long-term safety and tolerability of brexpiprazole (1 to 4 mg/day) in adolescent subjects, aged 13 to 17 years at the time of informed consent/assent, with a Diagnostic and Statistical Manual of Mental Disorders – Fifth Edition (DSM-5) diagnosis of schizophrenia. Enrollment into the trial will be drawn from eligible subjects who, in the investigator's judgment, could potentially benefit from monotherapy treatment with oral brexpiprazole for schizophrenia and will include rollover subjects from the double-blind, phase 3 efficacy Trial 331-10-234 and de novo subjects from select sites. De novo subjects must have a Kiddie Schedule for Affective Disorders and Schizophrenia - Present and Lifetime version (K-SADS-PL) confirmed DSM-5 diagnosis of schizophrenia. Subjects who roll over from Trial 331-10-234 who turned 18 years old during that trial are also permitted to enroll in Trial 331-10-236. The trial will be conducted on an outpatient basis.

Rollover subjects are restricted to those who are able to rollover within \leq 7 days of the Week 6 visit of Trial 331-10-234. Subjects who are only able to rollover from Trial 331-10-234 after $>$ 7 days from the Week 6 visit may be allowed to enter Trial 331-10-236 as de novo subjects following approval by the medical monitor.

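### SAP 10.1 sets a rollover subject's first open-label dose date at the day after the Week 6 visit, which is not true of delayed rollovers and conflicts with the SAP's other first-dose definitions

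*SAP*

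**What the plan says.** **The rule.** SAP 10.1 uses trial day for listings and for "determining whether an AE is a TEAE relative to the trial period". The formula is "Trial day = assessment date – first dose date + 1, for assessment date" on or after the first dose. It says that the term first dose date "refers to the first dose date for the open-label treatment". It then gives the rule for rollovers: "for a rollover subject the first dose date is the next day after the last assessment visit", identified as the parent-trial Week 6 visit. The rule has no exception and does not mention the recorded dosing date.

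**The rollover allowance.** SAP 3 says "Rollover subjects are restricted to those who are able to rollover within" 7 days of the Week 6 visit. Protocol 3.1 says "Rollover subjects will be considered as those who are able to rollover within" the same limit. Rollover inclusion criterion 4 (protocol Table 3.4.2.1-1) says "The baseline visit for Trial 331-10-236 coincides with the Week 6 visit of Trial 331-10-234", but sends a subject to the de novo route only if the visit cannot be done within 7 days.

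**The dosing anchor.** Protocol 3.2.1 says "The first dose of open-label brexpiprazole will be taken 1 day after the last dose of double-blind IMP". It expects that last dose on the Week 6 visit day where feasible, but does not require it.

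**How the date is used elsewhere.** SAP 8.1.1 counts a new event as a TEAE if it begins after the first IMP dose of the open-label period. SAP 8.4.1 counts exposure from the date of that dose. Under SAP 10.2, efficacy parameters and the three EPS scales are assigned to analysis visits by the trial-day windows of Table 10.2-1. Other parameters keep their recorded scheduled visit, and only their unscheduled records are windowed. If several records fall in one window, the last is summarised and all are listed.

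**The concern.** The rollover rule in SAP 10.1 is true only if the subject takes the last double-blind dose on the Week 6 visit day and starts open-label drug the next day. Both documents admit rollover subjects for whom this need not be so. For them the SAP holds two Day 1s: Week 6 plus one day in 10.1, and the actual first open-label dose in 8.1.1 and 8.4.1.

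Two outputs are at stake. The first is the TEAE count, which is part of the primary outcome: an event that starts in the gap before the first open-label dose would get a trial day of 1 or more and be classed as treatment-emergent. The second is the early by-visit summary of the EPS scales, where a shifted trial day can move a record into the next window and displace a value.

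**Working it through.** **Inputs.** Week 1, Week 2 and Week 4 targets are Days 7, 14 and 28, each ±3. The SAP windows are 2 to 10, 11 to 20 and 21 to 44 (SAP Table 10.2-1). The rollover limit is 7 days (SAP 3, protocol 3.1).

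**Size of the shift.** Let W be the Week 6 date and F the actual first open-label dose date.
- SAP 10.1 trial day = date − (W + 1) + 1
- True trial day = date − F + 1
- Difference = F − (W + 1), called the delay

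For a rollover visit on W + 7, F = W + 7 if dosing starts that day, so the delay is 6. If dosing starts the day after, F = W + 8 and the delay is 7. The documents do not say which applies.

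**Check at delay 0.** All 14 scheduled visits after Day 1, across their full ±3-day ranges, fall in their own window. The table works as intended when Day 1 is right.

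**Effect of delay.** SAP trial day = true trial day + delay. The permitted true days are 4 to 10 for Week 1 and 11 to 17 for Week 2.

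| Delay (days) | Week 1 days landing in Week 2 | Week 2 days landing in Week 4 |
|---|---|---|
| 1 | 1 of 7 | 0 of 7 |
| 2 | 2 of 7 | 0 of 7 |
| 3 | 3 of 7 | 0 of 7 |
| 4 | 4 of 7 | 1 of 7 |
| 5 | 5 of 7 | 2 of 7 |
| 6 | 6 of 7 | 3 of 7 |
| 7 | 7 of 7 | 4 of 7 |

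For on-target visits:
- At delays of 4 to 6, Week 1 becomes 7 + 4 to 7 + 6 = Day 11 to 13, and Week 2 becomes 14 + 4 to 14 + 6 = Day 18 to 20. Both are in the Week 2 window, so only the true Week 2 value is summarised and Week 1 is empty.
- At delay 7, Week 1 becomes Day 14 (Week 2 window) and Week 2 becomes Day 21 (Week 4 window).

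**Later visits.** At the latest permitted day and delay 7, Week 4 is 28 + 3 + 7 = 38, within 44. The tightest case is Month 3: 93 + 3 + 7 = 103, within 104. No scheduled visit from Week 4 to Month 24 is misassigned.

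**Which data this touches.** SAS, AIMS and BARS are rated at Weeks 1 and 2 and are windowed. CGAS is rated at Weeks 1 and 2 too, but is not among the five efficacy variables in SAP 9.1, so it is affected only if it is windowed. PANSS and CGI start at Week 4. Unscheduled records of any parameter in the early weeks can move.

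**TEAEs.** An event with onset from W + 1 up to the day before F gets SAP trial day 1 to delay, although it precedes the first open-label dose. It enters the count only if recorded in this trial, and recording starts at signature of this trial's consent form (protocol 3.7.1.1.1).

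**The opposite case.** If the last double-blind dose was the day before Week 6, protocol 3.2.1 puts F on the Week 6 day. SAP 10.1 labels that day −1, so an event starting after that dose on that day would be missed. A Week 2 visit on true Day 11 would become Day 10 and fall in the Week 1 window.

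**The case against.** The best defence is that the rollover clause only describes the planned schedule. The sentence before it points to the open-label first dose, and 8.1.1 and 8.4.1 agree. The protocol places baseline at the Week 6 visit and expects dosing to continue the next day. A programmer who takes those texts as governing makes no error. This has force: the error arises only if the clause is applied literally. But the clause is the only operational rule given for rollovers, and it is stated without exception, so the SAP leaves two answers open.

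The defence also limits the consequences, and these limits stand:
- A reader might infer that early PANSS or CGI results are misplaced. They are not: both start at Week 4, where no scheduled visit moves.
- A reader might infer that Week 1 data are lost. They leave the by-visit summary only. The listings keep them, and the last-visit LOCF summary is unchanged for anyone with later data.
- A reader might infer that TEAEs are over-counted for every delayed rollover. That needs consent signed before a delayed first dose and an event in the gap. If consent is itself signed at the delayed visit, earlier gap events are not collected in this trial.
- A reader might extend the error to de novo subjects who went through conversion. None is shown: their open-label Day 1 visit coincides with the end of conversion, and dosing follows the baseline evaluations, as SAP 10.1 says.

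**Conclusion.** The point holds as a contradiction within the SAP, and between the SAP and the protocol. The clause is a stated rule that gives wrong trial days for some permitted rollovers, so it should be corrected before programming.

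The size rests on two assumptions: that the clause is applied literally, and that the first dose slips with the rollover visit. Under those, trial day is too high by at most 6 or 7 days, depending on whether dosing starts on the delayed visit day or the day after. The effect is confined to events recorded in the gap before the first open-label dose and to windowed records around Weeks 1 and 2. Neither document gives the number of delayed rollovers or the length of their delays, so the overall impact cannot be sized. It is probably small in this descriptive trial, and the documents do not support a claim that the primary safety results are materially distorted.

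**What to change.** In SAP 10.1, replace the rollover clause with: *First dose date is the recorded date of the first open-label brexpiprazole dose.* Use that date for trial day, TEAE status, the Table 10.2-1 windows and the Day 1 origin of the Kaplan-Meier curves in 8.1.1. All then agree with exposure in 8.4.1. With that origin the delay is 0 by definition, and none of the 14 scheduled visits is misassigned.

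The cost is one sentence. The date is already needed for exposure, so no new data are required.

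Separately, the sponsor should reconcile the 7-day rollover allowance with the protocol 3.2.1 text that has open-label treatment follow the last double-blind dose with no break. As they stand, the two do not show how dosing is handled in a delayed rollover.
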